Telemonitoring with hand-held home spirometry has been shown to be a reliable and valuable tool for monitoring health in respiratory illnesses. Russell demonstrated that daily measurement of FVC in IPF patients is more sensitive than hospital-based measures in predicting prognosis and at time points earlier than had been possible with traditional periodic monitoring (16). Respiratory patients benefit from home spirometry use by predicting re-exacerbation (17), allowing earlier tapering of steroids (18), and decreased healthcare costs in both compliant and non-compliant cystic fibrosis patients. (19) Asthma patients reported home use of spirometry was 'not complicated' and the vast majority remained interested in using a home system of monitoring their lung disease. (20)

Combined structured telephone calls with telemonitoring demonstrate further benefit across chronic care conditions including respiratory-related diseases. Celler demonstrated significant drops in healthcare expenditures, reduced admission rates to hospitals, and reductions in hospital stays among patients with COPD, CAD, HTN, DM, and asthma (21). Inglis completed a meta-analysis of 41 randomized clinical trials of heart failure patients and showed that structured telephone calls with non-invasive home monitoring reduced the risk of all-cause mortality and heart failure related hospitalizations as well as improved quality of life, overall disease knowledge, and self-care behavior (22).

We propose that structured telenursing with non-invasive remote monitoring of newly diagnosed IPF patients will, due to improved levels of patient education and understanding, decrease hospitalizations for respiratory illness, decrease visits to emergency centers or urgent care centers, increase compliance with therapies such as medication, oxygen, and rehab, and ultimately increase quality of life. This increased education and oversight of patients by nurses and nurse practitioners trained in the management of patients with Idiopathic Pulmonary Fibrosis will allow for earlier recognition of complications and exacerbations that we hypothesize will ultimately show an impact on mortality.

Hypothesis

Telenursing with or without remote monitoring will reduce the rate of hospitalization, and positively affect other variables, as compared to usual care (control group).

Endpoints

Primary Endpoint

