1. To determine if the total number of hospitalizations related to respiratory event is lower in the interactive arms (Arm 2 and Arm 3) than in the control group (Arm 1).

Secondary Endpoints

1. To recognize, evaluate, and treat respiratory events through telecommunications with or without remote monitoring before the requirement of hospitalization or result of death.
2. To improve compliance in multiple areas noteworthy to IPF patients as measured by various means during clinic appointments to help guide further understanding and education:
 - a. IPF medication compliance – by patient report/diary
 - b. Laboratory follow up – by patient report and collection of laboratory reports
 - c. Attendance in pulmonary rehab or other formal exercise program – by patient report and/or collection of rehabilitation records
 - d. Supplemental oxygen use – by patient report
 - e. Management of comorbidities
 - i. GERD – by patient report of medication use and lifestyle changes
 - ii. OSA – by collection of compliance reports of pap therapy, or notes of such contained in office notes
 - f. Vaccines – by patient report
3. To improve quality of life scores as demonstrated by QOL questionnaires
4. To compare hospitalization parameters of “time to first hospitalization”, length of stay, number of hospitalizations per individual, and outcomes (such as quality of life post-hospitalization), discharge status [alive, deceased], discharged to [home, hospice facility].
5. To improve patient knowledge of lung disease, treatments, and management as demonstrated by self-report
6. To compare measurements obtained by clinic spirometry and home spirometry and clinic pulse oximetry and home oximetry.

Exploratory Endpoints

Exploratory endpoints will be collected to determine if the activities related to telehealth and remote monitoring will positively affect physiology and mortality.

1. To evaluate the difference in forced vital capacity (FVC) from baseline/diagnosis among the groups and as stratified by class
2. To evaluate the difference in walk distance in six minutes from baseline/diagnosis among the groups and as stratified by class

3. To compare findings in annual echocardiography in regards to right ventricular size and function and pulmonary hypertension from baseline/diagnosis among the groups and as stratified by class
4. To evaluate mortality differences among the groups and as stratified by class

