300	0.25	0.19	0.15	0.77	0.58	0.84	0.38	0.90

At least 80% power for the joint treatment effect and the A3 vs A1 effect was achieved when the event rate was .25, .19, and .15 for the three arms, respectively. The power for the comparison between A2 and A1 was 0.38, which was the highest of all the situations considered.

Proposed statistical analysis plan for the primary endpoint

The primary endpoint will be an ordinal variable that is a composite of hospitalizations and death within one year of diagnosis. The categories of the ordinal variable will be: 0 hospitalizations & no death, 1 hospitalization & no death, ..., K hospitalizations & no death, and then death as the final category. This will order the patients from best to worst outcomes in a way that incorporates the possibility of death.

The primary endpoint will be analyzed with a cumulative probability ordinal regression model which includes treatment assignment indicators and relevant covariates, such as age, gender, race, and other measures of baseline disease severity like **time-since-diagnosis**. Continuous variables, such as age, will be included in the model with restricted cubic splines in order to allow for the possibility of a non-linear association with the outcome. Model diagnostics, such as DFBETAs, will be generated to identify overly influential observations.

Once the regression model diagnostics indicate the model is reasonably fit, the treatment effect will be tested with Wald statistics at the $\alpha=0.05$ type I error level. The first effect to be tested is the joint treatment effect. If the joint effect is significant, then A3 vs A1 and A2 vs A1 will be tested. If the joint effect is not significant, no additional pairwise comparisons will be tested. The sequential test strategy ensures that the type I error rate is preserved.

As a sensitivity analysis, we will analyze hospitalization rates (not the composite hospitalization and death) with a model similar to the one described above.

Every effort will be made to collect covariate information; however, if missing data exists in the analysis dataset, we will adjust the analysis described above and implement multiple imputation with predictive mean matching. At least 30 imputations will be generated.

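### The primary endpoint has two definitions that conflict on death and leave cause of admission ambiguous: a count of respiratory hospitalizations, and a one-year ordinal composite with death as the worst category

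*Combined protocol and SAP*

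**What the plan says.** The combined protocol and SAP describes the primary endpoint in two places.

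- **Endpoints, Primary Endpoint.** The single item is "To determine if the total number of hospitalizations related to respiratory event is lower in the interactive arms"; the comparator is Arm 1, usual care. Death is not mentioned and no time window is given.
- **Statistics, Proposed statistical analysis plan for the primary endpoint.** This section opens by defining the variable: "The primary endpoint will be an ordinal variable that is a composite of hospitalizations and death within one year of diagnosis". Categories run upward by number of hospitalizations among survivors, and death is the last category. The stated reason is: "This will order the patients from best to worst outcomes in a way that incorporates the possibility of death". The sensitivity analysis is described in these words: "we will analyze hospitalization rates (not the composite hospitalization and death) with a model similar to the one described above". No cause of admission is named for either analysis.

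Other sections bear on the reading:

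- **Exploratory Endpoints**, item 4: "To evaluate mortality differences among the groups and as stratified by class".
- **Secondary Endpoints**, item 4, compares "length of stay, number of hospitalizations per individual", with no cause stated.
- The rationale just before the Hypothesis expects the intervention to "decrease hospitalizations for respiratory illness". The **Hypothesis** itself says "Telenursing with or without remote monitoring will reduce the rate of hospitalization" and names no cause.
- The power simulation sets a one-year hospitalization event rate of 25% in usual care, also without a cause.
- **Data Collection** includes admission and discharge dates, admitting diagnosis and health status.

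**The concern.** The primary endpoint decides what the trial may conclude, and here two current sections of one document each claim that status for a different variable. The analysis plan does more than put the Endpoints item into operational form. It adds death as the worst outcome, and it moves hospitalization without death, the kind of outcome that the Endpoints section calls primary, to a sensitivity analysis.

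A significant composite could arise because fewer patients died in the interactive arms or, if the plan is read literally, because fewer had non-respiratory admissions. Neither would by itself establish that respiratory hospitalizations fell. Read literally, the sensitivity analysis does not close the gap either, because it is not limited to respiratory admissions.

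**Working it through.** **The two definitions compared**

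- Death: absent in Endpoints; worst category in the analysis plan. This is a conflict.
- Cause of admission: respiratory in Endpoints; not stated in the analysis plan. This is an ambiguity.
- Window: not stated in Endpoints; one year from diagnosis in the analysis plan. This completes the Endpoints item and does not contradict it.
- Hospitalization without death: primary in Endpoints; sensitivity analysis in the analysis plan.

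**The plan's own figures.** The power table belongs to a third variable, any hospitalization within a year, with death not modelled. For 300 per arm and risks .25/.19/.15 it states power of 0.84 (joint), 0.38 (arm 2 versus 1) and 0.90 (arm 3 versus 1). Simulated Wald tests with risks 0.25, 0.25 × 0.77 = 0.1925 and 0.25 × 0.58 = 0.145 give 0.833, 0.390 and 0.901. The table reproduces there, but it does not show which definition the 25% refers to.

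**Illustration of how far the definitions can diverge**

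Inputs:

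- 50 patients per arm (Study Design).
- 25% hospitalized at least once, taken as any cause (assumption; the power section states none).
- Respiratory share 77.3%, from the cohort cited in the background, applied per admission. That cohort's figure covers the course of the disease, not one year.
- One-year mortality D of 5%, 10% or 15%. This is an assumption; the documents give no such figure for this population.
- Death either independent of hospitalization (c = 1) or three times as likely in hospitalized patients (c = 3).
- Admission counts Poisson-gamma with dispersion 0.01, 1 or 2.

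Formulas, with d0 and d1 the death risks in never- and ever-hospitalized patients:

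- d1 = c × d0 and 0.75 × d0 + 0.25 × d1 = D.
- Patients above the best category: A = 50 × [1 − 0.75 × (1 − d0)].
- Share ranked by death: 50 × D / A.
- Patients with at least one respiratory admission: R. At dispersion 0.01 this is close to 50 × (1 − 0.75^0.773) = 10.0; at dispersion 2 it is 10.5.
- Share above best with no respiratory admission: (A − R) / A.
- Share whose final rank is not set by the respiratory count: 1 − R × (1 − d1) / A.

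Results at the settings that give the ends of the ranges:

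- D = 5%, c = 1: A = 50 × (1 − 0.75 × 0.95) = 14.4; ranked by death 2.5/14.4 = 17%. With R = 10.5, final rank not set by the respiratory count 1 − 10.5 × 0.95/14.4 = 31%.
- D = 5%, c = 3: d0 = 0.05/1.5 = 0.033; A = 13.75. With R = 10.5, no respiratory admission 3.26/13.75 = 24%.
- D = 15%, c = 1: A = 50 × (1 − 0.75 × 0.85) = 18.1. With R = 10.0, no respiratory admission 8.15/18.1 = 45%.
- D = 15%, c = 3: d0 = 0.10, d1 = 0.30; A = 16.25; ranked by death 7.5/16.25 = 46%. With R = 10.0, final rank not set by the respiratory count 1 − 7.0/16.25 = 57%; no respiratory admission 6.28/16.25 = 39%.

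In the last setting the gap between 57% and 39% is 10.0 × 0.30 = 3.0 patients per arm who had a respiratory admission and also died.

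If the composite counts respiratory admissions only, the number above best becomes 50 × D + R × (1 − d1). The share with no respiratory admission then runs from (11.94 − 10.49)/11.94 = 12% (D = 5%, c = 3) to (15.98 − 9.97)/15.98 = 38% (D = 15%, c = 1).

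**The case against.** The strongest reply is that the analysis section is headed as the plan for the primary endpoint, so it analyses the endpoint already named, and its bare use of hospitalizations is shorthand for respiratory ones. The rationale and Hypothesis show the same drop of the adjective within one page. On that reading, the sensitivity analysis is the Endpoints item without death. The reply has force on cause of admission, which is why that part is called ambiguous. It does not dispose of death: no shorthand turns a count of admissions into a scale with death at the top, and the document has no rule giving one section precedence.

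Three further objections stand. Listing mortality as exploratory is compatible with death also being a composite component. Placing death in the ranking is a reasonable choice, and the plan gives its reason. Which of the two targets to adopt is for the investigators to decide.

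Two stronger readings are tempting, and the documents do not support them.

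- A reader might infer that two definitions raise the false-positive rate above 5%. That would require the choice to stay open until data are seen. The analysis plan names one outcome, one joint Wald test at 0.05, pairwise tests only if that test is significant, and a labelled sensitivity analysis.
- A reader might take the 31–57% as patients who do not count on the respiratory endpoint. Some of them had a respiratory admission and then died, and the Endpoints item would count those admissions. The share with none is 24–45%.

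**Conclusion.** The inconsistency is real. On death the two sections conflict outright; on cause of admission the document is ambiguous; the window only needs to be stated in both places. As written, a positive primary analysis would not by itself support the Endpoints claim of fewer respiratory hospitalizations.

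Under the assumptions above, 14–18 patients per arm of 50 would sit above the best composite category. Death would set the rank of 17–46% of them. About 24–45% would have no respiratory admission, or 12–38% of a smaller group if only respiratory admissions count. These figures are illustrative: the 5–15% mortality is assumed and drives most of the range, and both the 77.3% share and the any-cause reading of 25% are carried over to a one-year window. The finding itself rests on the wording and needs none of these numbers.

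**What to change.** Before outcome data are examined:

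1. State one primary endpoint in identical terms in the Endpoints section and the analysis plan, covering cause of admission, handling of death, and the window with its starting point.
2. If the composite is kept, reword the Endpoints claim to include death. A significant composite could still reflect deaths, so the conclusion must say so.
3. Make the hospitalization-only sensitivity analysis explicitly respiratory, using a prespecified rule applied to the admitting diagnosis.
4. Report respiratory hospitalizations, all-cause hospitalizations and deaths separately by arm.
5. State which definition the 25% planning rate refers to.

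The cost is wording in the two sections, a definition for the planning rate and one classification rule; admission dates, admitting diagnosis and vital status are already collected. Limiting the endpoint to respiratory admissions would leave somewhat fewer events. Under the same assumptions about 9.7–10.5 patients per arm would be hospitalized (50 × 0.25 × 0.773 = 9.7 if the share is per patient; 10.0–10.5 if per admission), against 50 × 0.25 = 12.5 for any cause. Classifying admissions, including those at local hospitals, takes some work.

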5. To evaluate patient management at ILD Center compared to outlying community centers among the groups and as stratified by class.
6. To evaluate a standardized protocol that includes a structured educational curriculum followed by a regularly timed disease-focused phone calls with protocolized interventions when disease progression is recognized.

Study Design

This is a single-center prospective randomized study to compare outcomes on hospitalization, healthcare compliance, and quality of life of telenursing with or without remote monitoring as compared to usual care. All patients diagnosed with IPF at the Vanderbilt Medical Center outpatient Pulmonary Clinic, who meet inclusion and exclusion criteria, will be asked to participate. Patients who agree to participate and sign consent will be randomized into one of three treatment arms: usual care (the control group), usual care with telenursing, usual care with telenursing and remote monitoring. Patients will be asked to participate in the study for at least one year. We expect to enroll 150 patients, or 50 patients into each arm.

Usual care (Arm 1) – Patients will continue to receive education in the clinic and telephonically about their lung disease, medications, and oxygen use. At the point of diagnosis, patients will be given our current educational materials to take home and review, as well as our contact information. Patients will continue to attend face-to-face visits in the out-patient setting. The frequency of visits will be based on the discretion of the provider. During these visits, the patient will continue to receive individualized standard of care, which may include some or all of the following: a face-to-face visit with a healthcare provider, vital signs, with pulse oximetry at rest, weight measurement, pulmonary function testing, a six-minute walk, and laboratory testing. Other testing, such as echocardiography or chest radiography, may be required based on need. If patients do not return to Vanderbilt Medical Center beyond the point of diagnosis, they will still be allowed to participate. The usual care of local healthcare providers will be collected.

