We generated 4000 replicates of the hypothetical study cohort for each combination of event rates, i.e., the rows of the results table. In each replicate, we calculated the (a) overall treatment effect, (b) the A2 vs A1 effect, and (c) the A3 vs A1 effect. The effect estimates were calculated by fitting a logistic regression model, and corresponding tests were calculated with the Wald method. Power was calculated as the proportion of the 4000 replicates in which the treatment effect was significant at $\alpha=0.05$ type I error rate.

Results

The results are provided in the table below. In the plot, RR refers to the relative risk of arm 3 to arm 1. In the table and in the plot, relative risk (RR) is simply the ratio of the risk in arm 2 (or 3) divided by the risk in arm 1.

Code

```
plotstyle(style = upright); par(mar = c(3,3,2,1))
plot.new()
plot.window(xlim = sim_settings$N %>% range, ylim = c(0,1))
g <- sim_settings %>%
  as.data.table %>%
  `[,`(,lines(copy(N), copy(power), type = "b"),p2)
axis(1, at = sim_settings$N %>% unique)
axis(2)
box()
title(xlab = "N (per arm)", ylab = "Power")
g <- sim_settings %>%
  filter(N == max(N)) %>%
  as.data.table %>%
  `[,`(, text(N, power, "RR = " %|% round(rr2,2), adj= c(1,-1)))
```

The table and plot report the same information.

Sample Size	A1 risk	A2 risk	A3 risk	RR 2:1	RR 3:1	Power 3:2:1	Power 2:1	Power 3:1
50	0.25	0.23	0.22	0.93	0.86	0.07	0.05	0.06
100	0.25	0.23	0.22	0.93	0.86	0.08	0.06	0.08
150	0.25	0.23	0.22	0.93	0.86	0.09	0.06	0.10
200	0.25	0.23	0.22	0.93	0.86	0.11	0.07	0.13
250	0.25	0.23	0.22	0.93	0.86	0.12	0.07	0.15
300	0.25	0.23	0.22	0.93	0.86	0.14	0.08	0.17
50	0.25	0.22	0.19	0.87	0.75	0.10	0.05	0.10
100	0.25	0.22	0.19	0.87	0.75	0.14	0.08	0.17
150	0.25	0.22	0.19	0.87	0.75	0.21	0.10	0.26
200	0.25	0.22	0.19	0.87	0.75	0.25	0.11	0.32
250	0.25	0.22	0.19	0.87	0.75	0.31	0.14	0.39
300	0.25	0.22	0.19	0.87	0.75	0.36	0.15	0.45

Sample Size	A1 risk	A2 risk	A3 risk	RR 2:1	RR 3:1	Power 3:2:1	Power 2:1	Power 3:1
50	0.25	0.20	0.16	0.82	0.66	0.16	0.08	0.17
100	0.25	0.20	0.16	0.82	0.66	0.24	0.12	0.31
150	0.25	0.20	0.16	0.82	0.66	0.36	0.15	0.44
200	0.25	0.20	0.16	0.82	0.66	0.46	0.19	0.55
250	0.25	0.20	0.16	0.82	0.66	0.56	0.24	0.66
300	0.25	0.20	0.16	0.82	0.66	0.64	0.27	0.73
50	0.25	0.19	0.15	0.77	0.58	0.21	0.09	0.23
100	0.25	0.19	0.15	0.77	0.58	0.38	0.16	0.46
150	0.25	0.19	0.15	0.77	0.58	0.53	0.23	0.64
200	0.25	0.19	0.15	0.77	0.58	0.66	0.29	0.74
250	0.25	0.19	0.15	0.77	0.58	0.75	0.33	0.83

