Power for proposed analysis. The proposed analysis is expected to be more powerful than the analysis simulated above because it uses an ordinal instead of a binary outcome. As such, the power calculations above serve as a lower bound for the analysis of the primary endpoint.

APPENDICES

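### At the planned 50 per arm, the joint-test power column is not reproduced by the Wald test that the plan says produced it: about 0.17 rather than 0.21 in the most favourable scenario

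*Combined protocol and SAP*

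**What the plan says.** Under Statistics, the Simulation section sets a one-year event rate of 25% in usual care and a range of rates in the other two arms. It then describes the method. "We generated 4000 replicates of the hypothetical study cohort for each combination of event rates", and in each one "we calculated the (a) overall treatment effect, (b) the A2 vs A1 effect, and (c) the A3 vs A1 effect". The estimates come from a logistic model, and "corresponding tests were calculated with the Wald method". Power is the share of significant replicates at a 0.05 level. No other test is named for the joint effect.

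The Results table gives joint power for arm sizes from 50 to 300. At 50 per arm it reads 0.07, 0.10, 0.16 and 0.21 across the four scenarios.

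Three other places use or depend on this column:

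- Study Design: "We expect to enroll 150 patients, or 50 patients into each arm".
- Proposed statistical analysis plan for the primary endpoint: "the treatment effect will be tested with Wald statistics". The joint effect is tested first, and the pairwise comparisons follow only if it is significant.
- Power for proposed analysis: the outcome to be analysed is ordinal rather than binary, and on that ground "the power calculations above serve as a lower bound for the analysis of the primary endpoint".

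**The concern.** The table has one stated method for three columns. If that method returns the two pairwise columns but not the joint column from the same inputs, the joint column came from something else. The joint test decides whether any arm comparison is made at all, so its power is the figure a reader would look up first, in the 50-per-arm rows. An overstated entry there misleads about the simulated analysis. It also weakens the lower-bound statement, which takes the tabled figures as its starting point.

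**Working it through.** **Inputs.** Control risk p1 = 0.25 (Simulation). Risks in arms 2 and 3 are 0.25 times the tabled relative risks, which are printed to two decimals; in the most favourable scenario p2 = 0.25 × 0.77 = 0.1925 and p3 = 0.25 × 0.58 = 0.145. Equal arms of size n, 4000 replicates, level 0.05.

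**Formulas.** With x_j events in arm j, let t_j = log(x_j/(n − x_j)) and v_j = x_j(n − x_j)/n.

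- Joint logistic Wald: Q = Σ v_j (t_j − t̄)², with t̄ the v-weighted mean; reject if Q > 5.991 (chi-square, 2 df).
- Pairwise Wald: (t_j − t_1)²/(1/v_j + 1/v_1); reject if above 3.841 (1 df).
- Joint likelihood ratio: twice the gain in binomial log-likelihood of three separate risks over one common risk; reject if above 5.991.

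Power is the sum of binomial probabilities over all outcomes (x1, x2, x3) that reject, so the recalculation has no simulation error. An arm with no events is counted as non-significant for Wald; its probability is at most about 0.855^50 = 0.0004 in the rows below.

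**Step 1: reproduce what can be reproduced.** Pairwise Wald at 50 per arm in the most favourable scenario is 0.095 (2:1) and 0.238 (3:1), against the tabled 0.09 and 0.23. Over all 24 rows, allowing for rounding, the Wald misfit chi-squares are 8.8 and 7.7. A likelihood-ratio test fits these two columns worse (25.9 and 53.7). So the inputs are right and the pairwise columns agree with the stated method.

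**Step 2: joint column at 50 per arm.**

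| RR 2:1 / 3:1 | Table | Wald | Likelihood ratio |
|---|---|---|---|
| 0.93 / 0.86 | 0.07 | 0.053 | 0.067 |
| 0.87 / 0.75 | 0.10 | 0.081 | 0.101 |
| 0.82 / 0.66 | 0.16 | 0.120 | 0.150 |
| 0.77 / 0.58 | 0.21 | 0.171 | 0.214 |

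The Monte Carlo SE in the last row is √(0.171 × 0.829/4000) = 0.006, so the gap is (0.21 − 0.171)/0.006, about 6.5 SE. Taking the table entry as low as 0.205 still leaves 5.7 SE. All four rows miss in the same direction, by 4.5 SE or more as printed.

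**Step 3: larger arms.** At 100 per arm Wald gives 0.07, 0.14, 0.23 and 0.35 (0.353), against the tabled 0.08, 0.14, 0.24 and 0.38; only the last is clearly off. From 150 per arm up no row is more than 0.02 away. At 300 per arm in the most favourable scenario Wald gives 0.835 against 0.84.

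**Step 4: could inputs explain it?** Over arm 2 and 3 risks consistent with the printed relative risks, the last 50-per-arm row moves only between 0.167 and 0.175. Reaching 0.21 needs p3 of about 0.132, and that would put 3:1 power near 0.30, against the tabled 0.23. Random arm sizes give 0.170.

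**Step 5: what does fit?** Over the 24 joint rows the misfit chi-square is 127 for Wald and 4.1 for likelihood ratio (largest gap 0.014). A score test gives 14.5, and 0.198 in the last 50-per-arm row. The direction is as expected: with all risks equal to 0.25 and 50 per arm, the joint Wald test rejects in 0.043 of samples and the likelihood-ratio test in 0.053.

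**The case against.** The strongest reply is that nothing the plan concludes changes. The only power conclusion in the Results text is that the joint effect passes 80% in the 0.25/0.19/0.15 scenario. That is the 300-per-arm row, and it survives. The text never cites a 50-per-arm joint figure as the trial's power, and 0.17 and 0.21 are both far below any usual target. All of this stands. It limits the consequence, but it does not make the column agree with its stated method.

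The discrepancy is also narrow: three of 24 rows are off by more than 0.02, two at 50 per arm and one at 100. That stands too, although the rows affected include those for the planned size.

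Two stronger readings are tempting and are not supported. A reader might infer that the planned primary analysis has joint power of 0.17, or that its power is overstated. The plan analyses an ordinal composite with covariates, and the recalculation is for the binary logistic model only. The ordinal analysis may do better, and nothing here measures by how much. A reader might also take it as established that a likelihood-ratio test was run. The protocol prints only plotting code, and a score test comes fairly close, so this remains an inference from fit.

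**Conclusion.** The point holds for the binary simulation. At 50 per arm the joint column is above the power of the described Wald test in all four scenarios, by about 0.02 to 0.04, or roughly a quarter to a third in relative terms. At 100 per arm the only clear miss is 0.38 against 0.35. The rest of the column is close.

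The tabled joint figures at the planned size therefore cannot be a lower bound derived from the Wald analysis described. Whether they happen to lie below the power of the planned ordinal analysis is open. The low power at 50 per arm does not come from this error: it is plain from the table as printed.

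The result assumes arm risks equal to 0.25 times the printed relative risks, equal arms, a logistic model with arm indicators only, and a 2-df chi-square reference. The finding that the column is not the stated Wald test does not depend on which other test was used.

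**What to change.** Recompute the Power 3:2:1 column with the Wald test. In the table's scenario order, the 50-per-arm rows become 0.05, 0.08, 0.12 and 0.17, and the 100-per-arm rows 0.07, 0.14, 0.23 and 0.35. If another test produced the column and is the one intended, name it in the Simulation section and align the test in the primary-endpoint analysis plan with it. In either case, base the lower-bound sentence on the corrected figures, or support it with a simulation of the ordinal model itself.

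The cost is one rerun of an existing simulation and one edited column, or two edited sentences if another test is named. Trial conduct is unaffected. With the Wald correction, the stated power becomes slightly less favourable.
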